1.3 Nonclinical Studies

Detailed information regarding the nonclinical pharmacology and toxicology of CT-P17 can be found in the investigator's brochure (IB).

1.4 Clinical Studies

No clinical studies of CT-P17 have been performed. The safety, tolerability, and pharmacokinetics (PK) of Humira (adalimumab) in healthy subjects were evaluated in a series of phase 1 studies.

Study DE024 was a single center, double-blind, randomized, placebo-controlled, parallel-group, ascending single-dose study in healthy male subjects. A total of 80 subjects (60 active and 20 placebo) participated in the study. Active subjects received a single intravenous (IV) dose of 1 mg/kg Humira over 2 to 3 minutes or 0.1, 0.3, and 1 mg/kg Humira via SC injection. Results demonstrated that following SC administration of Humira the mean

maximum observed serum concentration (C_{\max}) and area under the concentration-time curve (AUC) from zero to infinity ($AUC_{0-\infty}$) increased with increasing dose, with dose proportional increases noted at the 0.3 and 1 mg/kg SC doses only. The time to C_{\max} (T_{\max}) ranged from 48 to 336 hours and the mean half-lives ranged from 284 to 433 hours across doses.

Study DE015 was an open-label, randomized, parallel-group, single-dose study to assess the absolute and relative bioavailability of three injectable formulations of human anti-TNF antibody D2E7 in healthy male and female subjects. Subjects received 40 mg D2E7 as three different formulations via IV (50 mg/mL D2E7, with Tween-80) or SC injection (25 mg/mL D2E7, without Tween-80; 50 mg/mL D2E7, with Tween-80; and 50 mg/mL D2E7, without Tween-80). The results indicated that the mean C_{\max} and T_{\max} for the three SC formulations of D2E7 were comparable. The overview and results of Studies DE024 and DE015 can be found in *Clinical Pharmacology and Biopharmaceutics Review(s), FDA*.

Study M10-867 was a phase 1, single-dose, parallel-arm, single-blind, randomized study in healthy adult subjects. A total of 300 subjects were administered two formulations of Humira (40 mg/0.8 mL [50 mg/mL], reference vs. 40 mg/0.4 mL [100 mg/mL], test). The 90% CIs for the ratio of C_{\max} central values (101.9 – 115.2) and the ratio of AUC from time zero to 1344 hours (AUC_{0-1344}) central values (107.2 – 124.9) demonstrated comparable bioavailability of the two formulations. The overview and results of Study M10-867 can be found in the Product Monograph of Humira (*HUMIRA Product Monograph 2018*).

An overview of the safety profile of Humira, including undesirable effects, can be found in the Humira Summary of Product Characteristics (SmPC), European Public Assessment Report (EPAR) for Humira, and United States Prescribing Information (USPI) for US-licensed Humira (*Humira SmPC 2018; EMA EPAR for Humira 2017; Humira USPI 2018*).

1.5 Rationale for Study

The introduction of biosimilar (follow-on) medicinal products is desirable as they will enhance patient access by expanding the field of competing biotechnological treatments. The purpose of this study is to compare the PK, safety, and immunogenicity of the biosimilar test product (CT-P17) and the reference products (US-licensed Humira and EU-approved Humira) after a single SC injection of 40 mg of each product to healthy subjects following the recommendations of the guidance for industry, “Scientific Considerations in Demonstrating Biosimilarity with a Reference Product” (*DHHS 2015*).

The dose of Humira (40 mg) selected for this study is in line with the approved labeling for Humira (*Humira SmPC 2018; Humira USPI 2018*).

The study will be conducted in healthy subjects to avoid potentially high variability of the exposure of adalimumab if administered to patients with underlying and/or concomitant disease and concomitant medications. Due to the long half-life of adalimumab (approximately 2 weeks), a parallel-group design will be used in this study.

1.6 Risk–Benefit Assessment

Information about the risk following the administration of adalimumab was taken from the prescribing information for US-licensed Humira (*Humira USPI 2018*) and Humira SmPC for EU-approved Humira (*Humira SmPC 2018*). In view of the structural, biological, and toxicological similarity to Humira, CT-P17 is expected to display a similar safety profile.

The proposed safety screening and monitoring assessments are deemed to be sufficient to monitor potential risks of CT-P17 administration. Since adalimumab will be administered only once at the approved dosage of 40 mg, the overall risk of the study for healthy subjects is considered to be acceptable. No therapeutic benefit from adalimumab treatment is intended for the healthy subjects in this study.

2 Study Objectives

2.1 Primary Objective

- To demonstrate the PK similarity in terms of $AUC_{0-\text{inf}}$, $AUC_{0-\text{last}}$, and C_{\max} of CT-P17, US-licensed Humira, and EU-approved Humira in healthy subjects (CT-P17 to US-licensed Humira, CT-P17 to EU-approved Humira, and US-licensed Humira to EU-approved Humira)

2.2 Secondary Objective

- To evaluate the additional PK parameters, safety, and immunogenicity of CT-P17, US-licensed Humira, and EU-approved Humira in healthy subjects

[figure not shown]
3 Investigational Plan

3.1 Study Design

CT-P17 is being developed as a proposed biosimilar of Humira (adalimumab). This study is a phase 1, randomized, multicenter, double-blind, three-arm, parallel group, single-dose, active comparator study, which is designed to demonstrate equivalence in PK of CT-P17 to US-licensed Humira and EU-approved Humira in healthy subjects. Approximately 306 subjects will be enrolled and randomly assigned to one of the three treatment arms in a 1:1:1 ratio. In each treatment arm, all subjects will receive a single dose (40 mg) of either CT-P17, US-licensed Humira, or EU-approved Humira by SC injection via PFS on Day 1 followed by 10 weeks during which PK, safety, and immunogenicity measurements will be made. The randomization to treatment assignment will be stratified by body weight (≥ 80 kg vs. < 80 kg) as measured on Day -1, gender (male vs. female) and study center.

A schematic of the study design is presented in [Figure 3-1](#). Refer to [Section 3.2](#) for the study overview, including procedures to be performed during the study.

Figure 3-1 **Study Design Overview**

3.2 Study Overview

The study will include a Screening period, Admission, Study period, and End-of-Study (EOS) visit. All study procedures will be performed at the time points specified in the schedule of assessments ([Table 10-1](#)).

3.2.1 Screening Period (Day -28 to Day -2)

Subjects will sign and date the informed consent form and undergo procedures to determine eligibility. If necessary, a prescreening process may be carried out according to the standard operating procedures (SOP) of the study center.

During the screening period, retest for screening is permitted only once by the investigator's judgement. If the repeated test result is again not suitable or indeterminate for inclusion, the subject will be screen failed.

3.2.2 Admission (Day -1)

Eligible subjects will undergo baseline assessments: recheck of inclusion and exclusion criteria, medical history, adverse events (AEs), prior and concomitant medications, clinical signs and symptoms of TB, clinical laboratory tests, vital signs, body weight, physical examination, check for drug abuse, nicotine and alcohol and urine pregnancy test in women of childbearing potential.

Subject will be admitted to the study center, and will be randomized to receive either CT-P17, US-licensed Humira, or EU-approved Humira once all pertaining tests have been concluded to confirm the eligibility during Screening period and Day -1 (if it is concluded that the subject is not eligible in Day-1 assessments, the subject will be considered as screening failure even if they passed the screening).

3.2.3 Study Period (Day 1 to Day 71)

The study drug will be administered on the subject's lower abdomen except for the 5 cm around the subject's navel.

Subjects will be confined to the study center until completion of the 48-hour assessments after the administration of the study drug (Day 1) and admission can be extended depending on the subject's and study center's availability, up to Day 7. The consecutive study visits will be carried out on an out-patient basis.

Clinical laboratory testing and vital sign measurements, will be obtained during the study period. For **hypersensitivity monitoring, vital sign measurements** will be performed before the start of the study drug administration (within 15 minutes) and at 3, 6, 12, and 24 hours after the administration of the study drug on Day 1. The tolerance window for hypersensitivity monitoring is ± 30 minutes for 3 and 6 hours, and ± 60 minutes for 12 and 24 hours after the administration. **Either 3-lead or 12-lead electrocardiogram (ECG)** can be used for hypersensitivity monitoring at 3 hours (± 30 minutes) after the administration of the study drug on Day 1, and additional ECGs can be performed throughout the study if the subject experiences cardiac symptoms. **Local site pain** using 100 mm visual analogue scale (VAS) will be assessed immediately (within 15 minutes) after study drug administration (Day 1) and **injection site reactions** will be assessed 30 minutes (± 10 minutes) after study drug administration. A **physical examination** will be performed on Day 3. **Immunogenicity**

samples will be obtained in prior to the administration of the study drug on Day 1, and on Day 15, 29, 57 and 71. **Adverse events, concomitant medications, and clinical signs and symptoms of TB** will be monitored throughout the study. Blood samples for **PK analysis** will be collected from all subjects at the predefined time points in the following table:

PK sampling time points
Day 1 Pre-dose (within 60 minutes prior to administration of the study drug)
Day 1 (6 hours after the administration of the study drug); ± 15 minutes
Day 1 (12 hours after the administration of the study drug); ± 1 hour
Day 2 (24 hours after the administration of the study drug); ± 2 hours
Day 3, 4, 5, 5.5, 6, 6.5, 7, 8, and 9 (48, 72, 96, 108, 120, 132, 144, 168, and 192 hours, respectively, after the administration of the study drug); ± 2 hours
Day 15 and 22 (336 and 504 hours, respectively, after the administration of the study drug); ± 4 hours
Day 29, 43, 57, and 71 (i.e., EOS) after the administration of the study drug; ± 1 day

3.2.4 End-of-Study Visit (Day 71)

The EOS visit will be performed on Day 71. Subjects will return to the study center and undergo the following PK and safety assessments: PK and immunogenicity sampling for CT-P17, US-licensed Humira, and EU-approved Humira; collection of information related to AEs and concomitant medications; serum pregnancy tests in women of childbearing potential; TB monitoring and interferon- γ release assay (IGRA); vital signs; body weight; 12-lead ECG; clinical laboratory tests; and physical examination. The acceptable tolerance window for PK, safety, and immunogenicity assessments is ± 1 day for EOS (Day 71) assessments.

4 Study Population Selection and Withdrawal Criteria

Healthy male or female subjects 19 to 55 years of age, both inclusive, with a body mass index (BMI) between 18.0 and 29.9 kg/m², both inclusive, will be enrolled. Approximately 306 subjects (102 subjects in each arm) are planned to achieve at least 273 evaluable subjects (91 subjects in each arm).

4.1 Inclusion Criteria

Subjects who meet all of the following criteria will be considered eligible to participate in the clinical study:

1. Healthy male or female subjects, between the ages of 19 and 55 years, both inclusive (healthy is defined as no clinically relevant abnormalities identified by a detailed medical history, full physical examination, including blood pressure and heart rate measurement, 12-lead ECG, and clinical laboratory tests prior to the administration of the study drug).
2. Subject with C-reactive protein ≤ 1.5 times the upper limit of normal (ULN).
3. Subject has adequate liver function as determined by the following results:
 - Serum alanine aminotransferase (ALT) and aspartate aminotransferase (AST) $\leq 1.5 \times$ ULN and,
 - Total bilirubin $\leq 1.5 \times$ ULN.
4. Subject is informed and able to understand the full nature and purpose of the study, including possible risks and side effects, and is given ample time and opportunity to read and understand this information. The subject has the ability and agrees to cooperate with the investigator and must sign and date the written informed consent prior to performing any of the screening procedures.
5. BMI between 18.0 and 29.9 kg/m², both inclusive, when rounded to the nearest tenth
6. Subject and their partner of childbearing potential must agree to use a highly effective method of contraception as specified in [Section 5.8.2](#), throughout the study and for 5 months after the administration of assigned treatment. A man or woman is of childbearing potential if, in the opinion of the investigator, he or she is biologically capable of having children and is sexually active. Male and female subjects and their partners who have been surgically sterilized for less than 24 weeks prior to the date of informed consent must agree to use any medically acceptable methods of contraception. Menopausal

females must have experienced their last period more than 1 year prior to the date of informed consent to be classified as not of childbearing potential.

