5.8.2 Contraception

- Subject and their partner of childbearing potential must agree to use a highly effective method of contraception throughout the study and for 5 months after the administration of assigned treatment. Examples include the following:
 - Combined (estrogen and progestogen containing) or progestogen-only hormonal contraception associated with inhibition of ovulation
 - Intrauterine devices
 - True abstinence, when this is in line with the preferred and usual lifestyle of the subject. Periodic abstinence (e.g., calendar, ovulation, symptothermal, post-ovulation methods), declaration of abstinence for the duration of exposure to investigational drug, and withdrawal are not acceptable methods of contraception.
- A man or woman is of childbearing potential if, in the opinion of the investigator, he or she is biologically capable of having children and is sexually active. Male and female subjects and their partners who have been surgically sterilized for less than 24 weeks prior to the date of informed consent must agree to use any medically acceptable methods of contraception. Menopausal females must have experienced their last period more than 1 year prior to the date of informed consent to be classified as not of childbearing potential.

- Male subjects are not permitted to donate sperm or father a child within 5 months after administration of study drug.

6 Study Assessments and Procedures

Before performing any study procedures, all potential subjects will sign and date an ICF. The investigator will address all questions raised by the subject before the subject signs the ICF. The investigator will also sign and date the ICF. Subjects will undergo study procedures at the time points specified in the schedule of assessments ([Table 10-1](#)).

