6.2.2.8 Pregnancy

A serum pregnancy test (β -human chorionic gonadotropin) will be performed on women of childbearing potential at Screening and EOS, as indicated in the schedule of assessments ([Table 10-1](#)). A urine pregnancy test will be performed on women of childbearing potential on Day -1. Only subjects with negative results for both serum pregnancy test at Screening and urine pregnancy test on Day -1 can be enrolled in the study.

Throughout the study, a urine pregnancy test will be performed when there is any possibility of pregnancy, and a confirmatory serum pregnancy test will be performed if a urine pregnancy test result is positive.

In an event of unexpected pregnancy during study participation and for 5 months after administration of the study drug, the subjects will be counselled to inform the investigator. If a female subject or the partner of a male subject becomes pregnant, the pregnancy must be

reported to CELLTRION, Inc. and [REDACTED] PVG within 24 hours of the study center's knowledge of the pregnancy while confirmation is pending. The study center must complete the supplied pregnancy form (female subject or partner of a male subject) and return it to CELLTRION, Inc. and [REDACTED] PVG within 24 hours after acquisition of the consent for the pregnancy form.

Pregnant subjects or the pregnant partners of male subjects will be followed until the end of the pregnancy (e.g., delivery, stillbirth, miscarriage) and the mother and the baby will be followed for 1 year after the birth, provided consent is obtained. Pregnancy alone will not be regarded as an AE unless there is a suspicion that the study drug may have interfered with the effectiveness of a contraceptive medication. Elective abortions without complications should not be handled as AEs, unless they are therapeutic abortions. Hospitalization for normal delivery of a healthy newborn should not be considered as SAE. Any SAE that occurs during pregnancy (e.g., maternal serious complications, therapeutic abortion, ectopic pregnancy, stillbirth, neonatal death, congenital anomaly, birth defect) must be reported within 24 hours in accordance with the procedure for reporting SAEs ([Section 6.2.1.4](#)).

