6.3.1.3 Clinical Laboratory Testing

Blood samples for routine safety (clinical laboratory testing) will be collected for analysis throughout the study at the time points specified in the schedule of assessments ([Table 10-1](#)).

An additional blood for hepatitis B and C, HIV (HIV-1, HIV-2) and nontreponemal tests will also be required at Screening. A serum pregnancy test sample will be required at Screening and at the EOS visit for women of childbearing potential who have not been surgically sterilized.

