7.1. Demographics

Demographics and baseline characteristics will be summarized for the ITT and Safety populations by treatment arm and overall. The demographic characteristics will consist of age (years), gender (male, and female), ethnicity (Hispanic or Latino, Not Hispanic or Latino, Not Reported, and Unknown), and race (American Indian or Alaska Native, Asian, Black or African American, White, Other, and Multi-racial). Subjects who are from multiple races will be only counted in “Multi-racial” category and will not be counted in each specific race category. The baseline characteristics consist of whether New York Heart Association (NYHA) Functional Classification assessment was performed (yes or no), whether subject had any cardiac disease which can be classified by NYHA Functional Classification (yes or no), NYHA class (NYHA Class I, NYHA Class II, NYHA Class III, and NYHA Class IV), height (cm), weight (kg), and body mass index (BMI) (kg/m^2) which are measured at Screening, and weight category (body weight <80 kg and body weight ≥ 80 kg) which is measured on Day -1. For female subjects, female fertility status (surgically sterilized, post-menopausal, potentially able to bear children) will be presented.

Subject demographic and baseline characteristics will be presented in a data listing for the ITT population. The NYHA Functional Classification performed at Screening will be provided in a separate listing for the ITT population.

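### The definition of childbearing potential includes sexual activity, so a fertile woman judged inactive falls outside the scheduled pregnancy tests and the contraception commitment, in conflict with the protocol's own abstinence clauses

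*Protocol*

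**What the plan says.** Inclusion criterion 6 (Protocol synopsis and Section 4.1), repeated in Section 5.8.2, sets two joint conditions for childbearing potential, both in the investigator's opinion: "he or she is biologically capable of having children and is sexually active". The wording covers men as well as women.

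Three things depend on that definition:

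- **Contraception.** "Subject and their partner of childbearing potential must agree to use a highly effective method of contraception", during the study and for 5 months after dosing (Sections 4.1 and 5.8.2).
- **Serum pregnancy test.** Under Section 6.2.2.8 this "will be performed on women of childbearing potential at Screening and EOS". Section 3.2.4 and footnote 8 of Table 10-1 carry the same restriction. Section 6.3.1.3 narrows it further, to a sample "for women of childbearing potential who have not been surgically sterilized".
- **Urine pregnancy test.** "A urine pregnancy test will be performed on women of childbearing potential on Day -1" (Section 6.2.2.8, with the same restriction in Section 3.2.2 and footnote 8 of Table 10-1).

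Section 5.8.2 also has two clauses on abstinence. It accepts true abstinence as a highly effective method when that is how the subject prefers to live and usually lives. It then says that a "declaration of abstinence for the duration of exposure to investigational drug, and withdrawal are not acceptable methods of contraception".

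Exclusion criterion 5 (Section 4.2) bars women who are pregnant or are planning pregnancy within 5 months of dosing. Section 6.2.2.8 adds a urine test at any time when pregnancy is thought possible, with serum confirmation of a positive result.

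**The concern.** Pregnancy is an exclusion, and the protocol verifies it with two scheduled tests before dosing. Those tests reach only women who meet both parts of the definition. A woman who is biologically able to conceive but is judged not sexually active meets one part, so the plan as written asks for neither test. It also asks her for no contraception commitment for the 5 months that the protocol itself treats as relevant.

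The classification is a judgement in the present tense, and the documents do not say how the investigator should reach it. A woman who is inactive at Screening may already be pregnant, or her circumstances may change within the 5 months. The dose is single and cannot be withdrawn, and Section 1.5 gives adalimumab a half-life of about 2 weeks. What is at stake is subject protection and consistent eligibility decisions across centers, not the comparison of exposure.

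**Working it through.** The plan gives no figure on this point, so the check is to follow the term through the documents.

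**Step 1: who falls outside.** Childbearing potential requires biological capability and sexual activity, both in the investigator's opinion. If the second condition fails, the woman is not of childbearing potential. It follows that:

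- no Screening serum test and no Day -1 urine test are required (Section 6.2.2.8; Table 10-1, footnote 8);
- no end-of-study serum test is required (same places; Section 3.2.4);
- no contraception commitment is required (Sections 4.1 and 5.8.2).

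**Step 2: compare with the abstinence clauses of Section 5.8.2.** These clauses treat an abstinent person as someone who still needs an accepted method. Two cases matter:

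- *Abstinence is her usual way of life.* Section 5.8.2 would accept this as her method, so the contraception result is the same either way. The definition still removes her from the scheduled tests.
- *Abstinence is declared only for the exposure period.* Section 5.8.2 refuses this as a method. If the investigator nevertheless judges her not sexually active, the definition releases her from needing any method and from the tests. Here the two rules give opposite results.

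In both cases the abstinence clauses have almost nobody to apply to, because the definition has already taken abstinent women out of the group that needs a method.

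**Step 3: compare with the menopausal rule.** Inclusion 6 lets a menopausal woman be classified as not of childbearing potential only if her last period was more than 1 year before consent. That is a biological condition. A younger, fertile woman can lose the same classification on sexual activity alone. One criterion therefore uses two concepts.

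**Step 4: compare the testing passages with each other.** Section 6.3.1.3 exempts surgically sterilized women from the serum test. Section 6.2.2.8 and footnote 8 of Table 10-1 have no such exemption.

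**Step 5: do other sentences restore the tests?** Section 6.2.2.8 says that only subjects negative on both tests can be enrolled. Taken literally that would exclude every man, so in context it refers to the women already selected for testing. SAP Section 10.8 mentions the serum test without the restriction, but footnote 8 of SAP Appendix 14.1 restores it. These sentences add inconsistency and do not close the gap.

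**Step 6: size.** The count would be 306 × (share who are women) × (share of those who are fertile) × (share of those judged not sexually active). The documents give only the 306.

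**The case against.** The strongest reply is that Section 5.8.2 lists unacceptable methods for people already required to use one. It does not define childbearing potential. On that view there is tension rather than strict contradiction, and the near-redundant abstinence item is untidy drafting. This is fair as far as it goes: for a woman whose abstinence is her usual way of life, the contraception outcome does not change. It does not answer the case of abstinence declared only for the study, and it does not restore the missing tests in either case.

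The second reply is that safeguards exist. Exclusion 5 applies to every woman, including those planning pregnancy. A urine test follows whenever pregnancy is thought possible, and subjects are counselled to report pregnancy for 5 months after dosing. These reduce the risk. However, the unscheduled test depends on someone suspecting pregnancy, reporting comes after the event, and exclusion 5 has no other scheduled test to verify it.

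A reader might infer three stronger points that the documents do not support:

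- *A woman's own statement is enough to exempt her.* The criterion rests on the investigator's opinion. What she says is likely to weigh heavily, since no other basis is given, but it does not decide the matter.
- *The SAP uses a different denominator.* SAP Section 7.1 summarizes "female fertility status (surgically sterilized, post-menopausal, potentially able to bear children") as a descriptive characteristic, and Section 10.8 summarizes tests in women of childbearing potential. Whether these come from different case report form fields cannot be seen from the documents.
- *The sterilization exemption in Section 6.3.1.3 contradicts the 24-week clause in inclusion 6.* One concerns who gives a serum sample and the other who uses contraception. A woman can be exempt from the first and bound by the second. The real discrepancy is the one in Step 4.

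**Conclusion.** The point holds as an inconsistency that affects subject protection. As written, a fertile woman judged not sexually active can be dosed without either scheduled pregnancy test and without a contraception commitment. That result conflicts with the abstinence clauses of Section 5.8.2 and with the biological rule for menopausal women in inclusion 6. It rests on reading the definition and the testing passages literally, and on investigators applying them so.

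No headcount can be supported. It is tempting to take half of 306 as women (306 × 0.5 = 153), assume that 10–30% report no sexual activity, and arrive at 15–46. Both inputs are assumptions. The rate would also be applied to all women, although the age range is 19 to 55 years and some may be sterilized or post-menopausal. And it supposes that every such woman would be exempted. The finding does not depend on that figure.

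Sample size, power and the primary pharmacokinetic analysis are unaffected. The correction is worth making because it is cheap and concerns verification of an exclusion before an irreversible dose.

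**What to change.** Reconcile the synopsis, Section 4.1 (inclusion 6), Section 5.8.2, Section 6.2.2.8, Section 6.3.1.3 and footnote 8 of Table 10-1, so that:

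- one stated definition determines who has the Screening and Day -1 pregnancy tests already in Table 10-1;
- that definition agrees with the abstinence clauses of Section 5.8.2;
- the sterilization exemption in Section 6.3.1.3 is aligned with Section 6.2.2.8 and Table 10-1, which have none.

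The clinical rule is for the sponsor to decide. Simply deleting the reference to sexual activity may look like the obvious edit, but the definition also covers men and partners, so that would choose a rule and widen the contraception obligation beyond the women discussed here.

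The cost is a protocol amendment and possibly a few more routine tests of a kind the centers already perform. Depending on the definition chosen, some subjects may also come under a contraception obligation that they do not have now. No new procedure is needed.
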